6.6.1.2. Non-hematologic Toxicity

Table 6-6 Dose Modifications for Non-hematologic Toxicity

	Recommended Action					
Non-heme toxicity	Lenalidomide	Carfilzomib	Elotuzumab			
Non-Blistering Rash						
Grade 3	Hold lenalidomide dose; follow weekly If the toxicity resolves to ≤ Grade 1 prior to Day 21 of the current cycle, restart at 1 dose decrement and continue the cycle until Day 21 of the current cycle.	Hold (if Treating Investigator's opinion is possibly related to Carfilzomib) until ≤ Grade 1, reinstitute at current dose	Hold Upon resolution elotuzumab can be restarted at the treating physician's discretion			
Grade 4	Discontinue lenalidomide study drug.	Hold until \leq Grade 1, reinstitute at current dose.	Hold Upon resolution elotuzumab can be restarted at the treating physician's discretion			

Table 6-6 Dose Modifications for Non-hematologic Toxicity

Recommended Action					
Non-heme toxicity	Lenalidomide	Carfilzomib	Elotuzumab		
Desquamating (blistering) rash – any grade	Discontinue lenalidomide study drug.	Hold until ≤ Grade 1, reinstitute at current dose.	Hold Upon resolution elotuzumab can be restarted at the treating physician's discretion		
Erythema multiforme ≥ Grade 3	Discontinue lenalidomide study drug.	Hold until \leq Grade 1, reinstitute at current dose.	Hold Upon resolution elotuzumab can be restarted at the treating physician's discretion		
Sinus bradycardia/ other cardiac arrhythmia					
≤ Grade 2	Hold lenalidomide dose. Follow at least weekly. If the toxicity resolves to ≤ Grade 1 prior to Day 21, restart at 1 dose decrement and continue the cycle until Day 21.	Hold until ≤ Grade 1, reinstitute at current dose.	Hold Upon resolution elotuzumab can be restarted at the treating physician's discretion		
≥ Grade 3	Discontinue lenalidomide study drug	Hold until ≤ Grade 1, reinstitute at current dose.	Hold Upon resolution elotuzumab can be restarted at the treating physician's discretion		
Allergic reaction/hypersensitivity					
Grade 2 – 3	Hold lenalidomide dose. Follow at least weekly. If the toxicity resolves to ≤ Grade 1 prior to Day 21, restart at 1 dose decrement and continue the cycle until Day 21.	Hold until ≤ Grade 1, reinstitute at current dose.	Discontinue		
Grade 4	Discontinue	Discontinue	Discontinue		

Table 6-6 Dose Modifications for Non-hematologic Toxicity

	Recommended Action				
Non-heme toxicity	Lenalidomide	Carfilzomib	Elotuzumab		
Tumor lysis syndrome (≥ 3 of the following: ≥ 50% increase in creatinine, uric acid, or phosphate;≥ 30% increase in potassium;≥ 20% decrease in calcium; or ≥ 2-fold increase in LDH	Hold lenalidomide until all abnormalities in serum chemistries have resolved. Reinstitute at full doses.	Hold carfilzomib until all abnormalities in serum chemistries have resolved. Reinstitute at full doses.	Hold Upon resolution elotuzumab can be restarted at the treating physician's discretion		
Infection Grade 3 or 4	Hold lenalidomide until systemic treatment for infection is completed. If no neutropenia, restart lenalidomide at full dose. If neutropenic, follow neutropenic instructions.	Hold carfilzomib until systemic treatment for infection is completed If no neutropenia, restart carfilzomib at full dose. If neutropenic, follow neutropenic instructions.	Hold Upon resolution elotuzumab can be restarted at the treating physician's discretion		
Herpes zoster or simplex of any grade	Hold lenalidomide until lesions are dry. Reinstitute at full doses.	Hold carfilzomib until lesions are dry. Reinstitute at full doses.	Hold When lesions are dry elotuzumab can be restarted at the treating physician's discretion		
Grade 2 neuropathy with pain or any Grade 3 neuropathy	Hold until ≤ Grade 2. Then restart lenalidomide at 1 dose decrement	Withhold until toxicity is resolved or returned to baseline After resolution, consider if restarting CFZ at the same dose or at a reduced dose is appropriate. If tolerated, the reduced dose may be escalated to the previous dose at the discretion of the physician	Hold Upon resolution elotuzumab can be restarted at the treating physician's discretion		
Grade 4 neuropathy	Discontinue	Discontinue	Hold Upon resolution elotuzumab can be restarted at the treating physician's discretion		
Renal dysfunction					
Serum creatinine > 2 mg/dL	Base dose reduction on calculated GFR (below)	Base dose reduction on calculated GFR (below)	Hold Upon resolution elotuzumab can be		

Table 6-6 Dose Modifications for Non-hematologic Toxicity

	Recomme	nded Action	
Non-heme toxicity	Lenalidomide	Carfilzomib	Elotuzumab
			restarted at the treating physician's discretion
CrCl>60 mL/min	Full dose	Full dose	Full dose
CrCl <60 mL/min > 30 mL/min	Reduce lenalidomide to 10 mg every 24 h; may reinstate prior dose if, after 2 cycles, CrCl normalizes	Full dose	Full dose
CrCl< 30 mL/min	Reduce lenalidomide to 15 mg every 48 h	Hold carfilzomib until CrCl> 30 mL/min. If attributed to carfilzomib, restart at 1 dose decrement. If tolerated, the reduced dose may be escalated to the previous dose at the discretion of the physician. If not attributed to carfilzomib, restart at dose used prior to the event. Frequent monitoring of renal function should then be implemented	Full Dose
CrCl< 30 mL/min requiring dialysis	5 mg once daily. On dialysis days the dose should be administered following dialysis.	Hold until resolved to ≤ Grade 2. Then restart carfilzomib at 1 dose decrement	Full Dose

Table 6-6 Dose Modifications for Non-hematologic Toxicity

	Recomme	nded Action	
Non-heme toxicity	Lenalidomide	Carfilzomib	Elotuzumab
Venous thrombosis/embolism ≥ Grade 3	Hold lenalidomide dose and adjust anticoagulation regimen; re-start at Treating Investigator's discretion at full dose	No adjustment required	No adjustment required
Hyperthyroidism or hypothyroidism	Omit lenalidomide for remainder of cycle, evaluate, and initiate appropriate therapy. Restart lenalidomide next cycle at 1 dose decrement	No adjustment required	No adjustment required
Congestive heart failure (CHF)	Any subject with symptoms of CHF, whether or not lenalidomide related, must have the dose held until resolution or return to baseline. If CHF was felt to be lenalidomide related, reinstate by one dose decrement after return to baseline. If no resolution of CHF after 2 weeks, the subject will be withdrawn from the study.	Any subject with symptoms of CHF, whether or not carfilzomib related, must have the dose held until resolution or return to baseline. If CHF was felt to be carfilzomib related, reinstate by one dose decrement after return to baseline. If tolerated, the reduced dose may be escalated to the previous dose at the discretion of the physician. If no resolution of CHF after 2 weeks, the subject will be withdrawn from the study.	Hold Upon resolution elotuzumab can be restarted at the treating physician's discretion
Hypertension including Hypertensive Crises	NA	≥ Grade 3: Carfilzomib attribution, hold drug until resolved to ≤ Grade 2. Resume at one level dose reduction	NA

Table 6-6 Dose Modifications for Non-hematologic Toxicity

	Recomm	ended Action	
Non-heme toxicity	Lenalidomide	Carfilzomib	Elotuzumab
Heart problems, including rapid, strong, or irregular heartbeat, heart attack, reduced blood flow to the heart, abnormal amount of fluid to the lining around the heart, and swelling/irritation of the lining around the heart	NA	≥ Grade 3: Carfilzomib attribution, hold drug until resolved to ≤ Grade 1. Resume at one level dose reduction	NA
Pericardial Effusion	NA	≥ Grade 3: Carfilzomib attribution, hold drug until resolved to Grade 1. Resume at one level dose reduction	NA
Pericarditis	NA	≥ Grade 3: Carfilzomib attribution, hold drug until resolved to Grade 1. Resume at one level dose reduction	NA
Pulmonary Hypertension	NA	≥ Grade 3: Carfilzomib attribution, hold drug until resolved to baseline. After resolution consider if restarting CFZ at the same dose or reduced dose is appropriate. If tolerated, the reduced dose may be escalated to the previous dose at the discretion of the physician.	NA
Pulmonary Toxicities: Interstitial Lung Disease (inc. pneumonitis), Acute Respiratory Failure, and Adult Respiratory Distress Syndrome (ARDS), cough and cough with phlegm	NA	 ≥ Grade 2 for Pneumonitis ≥ Grade 3 for ARDS ≥ Grade 4 for Respiratory Failure Carfilzomib attribution, hold drug until resolved to ≤Grade 1. Resume at one level dose reduction 	NA

Table 6-6 Dose Modifications for Non-hematologic Toxicity

Recommended Action			
Non-heme toxicity	Lenalidomide	Carfilzomib	Elotuzumab
Blood clot in the lungs, fluid in the lungs, bleeding in the lungs	NA	≥ Grade 3: Carfilzomib attribution, hold drug until resolved to ≤ Grade 1. Resume at one level dose reduction	NA
Gastrointestinal Perforation	NA	≥ Grade 3: Carfilzomib attribution, hold drug until resolved to Grade 1. Resume at one level dose reduction	NA
Hepatic Toxicities (≥ Grade 3 elevation of AST or ALT, Bilirrubin, or other ≥ Grade 3 liver abnormalities)	Hold drug until resolved to ≤Grade 1 or baseline. Resume at the same dose or reduced dose as appropriate. If tolerated, the reduced dose may be escalated to the previous dose at the discretion of the physician. Frequent monitoring of liver function should then be implemented.	Hold drug until resolved to ≤Grade 1 or baseline. Resume at the same dose or reduced dose as appropriate. If tolerated, the reduced dose may be escalated to the previous dose at the discretion of the physician. Frequent monitoring of liver function should then be implemented.	Hold treatment and restart when toxicity has resolved to ≤ Grade 1 or baseline
Other non-hematologic toxicity assessed as lenalidomide-related ≥ Grade 3	Hold lenalidomide dose. Follow at least weekly. If the toxicity ≤ Grade 1 before Day 21 of the current cycle, restart at 1 dose decrement and continue until Day 21 of the current cycle	Full dose	Full dose

Table 6-6 Dose Modifications for Non-hematologic Toxicity

Recommended Action			
Non-heme toxicity	Lenalidomide	Carfilzomib	Elotuzumab
Other non-hematologic toxicity assessed as carfilzomib-related ≥ Grade 3	Full dose	Hold carfilzomib dose until toxicity resolves to ≤ Grade 1 or baseline. After resolution, consider if restarting CFZ at the same dose or at a reduced dose as appropriate. If tolerated, the reduced dose may be escalated to the previous dose at the discretion of the physician.	Full dose
Other non-hematologic toxicity assessed as elotuzumab-related ≥ Grade 3	Full dose	Full dose	Hold Upon resolution, restart at the treating physician's discretion
Other non-hematologic toxicity assessed as drug- related ≥ Grade 3	Hold treatment and restart at 1 dose decrement when toxicity has resolved to ≤ Grade 1 or baseline	Hold treatment and restart at 1 dose decrement when toxicity has resolved to ≤ Grade 1 or baseline	Hold treatment and restart when toxicity has resolved to ≤ Grade 1 or baseline

Table 6-8 Dose Modification Guidelines for Toxicity Related to Dexamethasone

BODY SYSTEM	SYMPTOM	RECOMMENDED ACTION	
Gastrointestinal	Dyspepsia, gastric or duodenal ulcer, gastritis Grade 1-2 (requiring medical management)	Treat with H2 blockers, sucralfate, or omeprazole. If symptoms persist despite above measures, decrease dexamethasone dose by 1 dose level.	
Gastrointestinal	≥ Grade 3 (requiring hospitalization or surgery)	Hold dexamethasone until symptoms adequately controlled. Restart at 1 dose decrement along with concurrent therapy with H2 blockers, sucralfate, or omeprazole. If symptoms persist despite above measures, discontinue dexamethasone permanently.	
Gastrointestinal	Acute pancreatitis	Discontinue dexamethasone permanently.	
Cardiovascular	Edema ≥ Grade 3 (limiting function and unresponsive to therapy or anasarca)	Diuretics as needed, and restart dexamethasone at 1 dose decrement; if edema persists despite above measures, decrease dose another level Discontinue dexamethasone permanently is symptoms persist despite second reduction.	
Neurology	Confusion or mood alteration	Hold dexamethasone until symptoms resolve. Restart at 1 dose decrement. If symptoms	

UCM IRB 16-1138

Elo-KRd Version 8 03/26/2020

	> Grade 2 (interfering with function +/-	persist despite above measures, discontinue	
	interfering with activities of daily	dexamethasone permanently.	
	living)		
Musculoskeletal	Muscle weakness > Grade 2	Decrease dexamethasone by 1 dose level. If	
	(symptomatic and interfering with	weakness persists, decrease dose by 1 more	
	function +/- interfering with activities	dose level. Discontinue dexamethasone	
	of daily living)	permanently if symptoms persist.	
Metabolic	Hyperglycemia ≥ Grade 3	Treatment with insulin or PO hypoglycemic	
		agents as needed. If uncontrolled despite above	
		measures, decrease dose by 1 dose level until	
		levels are satisfactory.	

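### Table 6-6 gives two carfilzomib restart doses for a carfilzomib-attributed Grade 3 or higher arrhythmia, and no text says which row prevails

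*Combined protocol and SAP*

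**What the plan says.** Section 6.6.1.2, Table 6-6, has a row headed "Sinus bradycardia/ other cardiac arrhythmia", split into Grade 2 or lower and Grade 3 or higher. At Grade 3 or higher lenalidomide is discontinued and elotuzumab is held, to be restarted at the physician's discretion. Carfilzomib gets an instruction that the table also uses in several other rows: "Hold until \leq Grade 1, reinstitute at current dose". It carries no condition on cause.

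Further down, the same table has a row that begins "Heart problems, including rapid, strong, or irregular heartbeat, heart attack, reduced blood flow to the heart". For Grade 3 or higher its carfilzomib cell reads "Carfilzomib attribution, hold drug until resolved to ≤ Grade 1. Resume at one level dose reduction". The lenalidomide and elotuzumab cells say NA.

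Three other places bear on which row applies:

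- Section 6.5 starts a new cycle one decrement lower if elotuzumab, carfilzomib or lenalidomide was held for the remainder of the previous cycle, or if residual toxicity delays the new cycle.
- Section 6.6 asks for discussion with the Lead Principal Investigator when a modification differs from those in the protocol.
- Sections 1.6 and 4.2 describe the dose modifications as aggressive, and as required or mandated.

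**The concern.** A Grade 3 or higher rapid or irregular rhythm that the investigator attributes to carfilzomib satisfies both rows. They agree on when to restart (Grade 1 or lower) but not on the dose. Two sites could therefore treat the same patient differently, each following the table. One of them would re-expose the patient to the unreduced dose of the drug blamed for a severe arrhythmia.

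The rows also disagree on the other drugs. A site that looks up the event under heart problems finds NA for lenalidomide and elotuzumab, where the arrhythmia row says discontinue and hold.

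**Working it through.** The plan states no figure to reproduce here. The check compares the table rows, looks for a rule that ranks them, and sizes the dose gap.

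**1. The two rows side by side (Table 6-6, Grade 3 or higher)**

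| | Arrhythmia row | Heart-problems row |
|---|---|---|
| Event | Sinus bradycardia or other arrhythmia | Heart problems, naming a rapid or irregular heartbeat |
| Attribution needed | None | Carfilzomib |
| Hold until | Grade 1 or lower | Grade 1 or lower |
| Carfilzomib restart | Current dose | One level lower |
| Lenalidomide | Discontinue | NA |
| Elotuzumab | Hold; restart at discretion | NA |

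The overlap needs Grade 3 or higher and carfilzomib attribution. It is clearest for a rapid or irregular rhythm. Sinus bradycardia falls in the second row only through the general term heart problems. If the event is not attributed to carfilzomib, only the first row applies and there is no conflict.

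**2. Does attribution settle it elsewhere in the table?** Not uniformly.

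- *Reduction.* Carfilzomib-related congestive heart failure restarts one decrement lower, with later re-escalation allowed. Attributed Grade 3 or higher hypertension, pericardial effusion and pericarditis all resume one level lower.
- *Choice.* For attributed pulmonary hypertension: "After resolution consider if restarting CFZ at the same dose or reduced dose is appropriate". For other carfilzomib-related toxicity: "consider if restarting CFZ at the same dose or at a reduced dose as appropriate".
- *Same dose.* The Grade 3 rash row makes the hold depend on the investigator's view of the cause and still restarts at the current dose: "opinion is possibly related to Carfilzomib) until ≤ Grade 1, reinstitute at current dose".
- *Both branches written out.* For creatinine clearance below 30 mL/min: "If attributed to carfilzomib, restart at 1 dose decrement", followed by the pre-event dose if the event is not attributed.

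**3. Which cases does Section 6.5 close?** Appendix 6, footnote 20, schedules carfilzomib on Days 1, 8 and 15 in cycles 1-8 and on Days 1 and 15 from cycle 9.

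- A hold that misses Day 15, or toxicity that delays the next Day 1, triggers the decrement. The conflict then does not matter for the new cycle.
- An event that resolves in time for Day 8 or Day 15 of the same cycle is not covered, and the two rows give different doses.
- An event after Day 15 that resolves before an undelayed next Day 1 misses no carfilzomib dose. Whether Section 6.5 applies is arguable.
- The arrhythmia row discontinues lenalidomide. If that counts as held for the remainder of the cycle (an assumption; the text does not say), the next cycle starts one decrement lower in any case. Section 6.5 does not say which drug takes that decrement.

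**4. Size per infusion.** Table 6-1 levels are 70, 56, 45, 36 and 27 mg/m². Gap = current level minus next level; percentage = gap divided by current level.

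- 70 to 56: 14 mg/m², 14/70 = 20.0%
- 56 to 45: 11 mg/m², 11/56 = 19.6%
- 45 to 36: 9 mg/m², 9/45 = 20.0%
- 36 to 27: 9 mg/m², 9/36 = 25.0%

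At the 2.2 m² cap (Section 6.4.2): 70 × 2.2 = 154 mg and 56 × 2.2 = 123.2 mg, a gap of 30.8 mg. Both capped doses match those printed in that section. The 20 mg/m² dose of cycle 1 Day 1 is not a Table 6-1 level, so no gap is given for it.

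**The case against.** The best defence is that the rows can be read together. The arrhythmia row is a general default. The heart-problems row, which requires attribution and says NA for the other drugs, is a carfilzomib-only supplement. On that reading the dose is the current one by default and one level lower if carfilzomib is to blame. The congestive heart failure, hypertension, pericardial effusion and pericarditis rows support it, and so does the stated aim of aggressive modification. This stands as the likely intent. It remains an inference: no sentence gives precedence to the specific, the attributed or the stricter row, and the rash, pulmonary hypertension and residual rows show that attribution does not always bring a reduction.

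Oversight also limits harm:

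- the investigator may discontinue the drug (Section 6.6);
- Grade 4 non-hematologic toxicity in two or more patients prompts DSMB review (Section 6.8);
- a fourth occurrence of the same Grade 3 or higher non-hematologic toxicity ends treatment (Section 6.9);
- serious events reach the Lead Principal Investigator within 24 hours (Section 8.3);
- a bi-weekly teleconference reviews safety and adherence (Section 13.7).

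These make divergence between sites less likely to go unnoticed, but none chooses between the rows. The Section 6.6 discussion requirement does not help either, because both doses are stated in the protocol. The column heading, which calls the actions recommended, softens the conflict, but Sections 1.6 and 4.2 call the modifications required and mandated.

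**Conclusion.** The inconsistency is real, narrow and worth correcting. It is a minor to moderate patient-safety point. It concerns a carfilzomib-attributed Grade 3 or higher arrhythmia that resolves in time for a dose within the cycle and, arguably, one after Day 15 that resolves before an undelayed next Day 1. The firm size is one Table 6-1 level per infusion, about 20% to 25%.

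A reader might infer more than the documents support:

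- *That restarting at the same dose is itself an error.* Other attributed rows allow it. The fault is two incompatible instructions for one event.
- *That the gap can be totalled over later cycles, or expressed as a share of scheduled infusions.* A running total depends on the unsettled reading of Section 6.5 and on no other dose change. A count of schedule days measures neither risk nor patients, and a count of within-cycle days would miss the window after Day 15.
- *That many patients are affected.* The documents give no arrhythmia rate in this setting. The number is not estimated and is probably small.
- *That the trial's conclusions are at risk.* Sample size, endpoints and analysis are unaffected.

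Confidence is high that the rows overlap and that nothing ranks them. It is lower on how long a dose difference would last.

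**What to change.** In the Grade 3 or higher arrhythmia row, replace the carfilzomib instruction with: *Hold until Grade 1 or lower. If attributed to carfilzomib, resume one dose level lower; otherwise reinstitute at current dose, subject to Section 6.5.* This follows the two-branch pattern of the creatinine clearance row. Keep the row's lenalidomide and elotuzumab actions.

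In the heart-problems row add: *For arrhythmia, see the arrhythmia row.* Its NA entries then no longer contradict the discontinue and hold instructions.

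The cost is one sentence and one cross-reference in a protocol amendment, with no change to the statistical plan.

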6.4.2. Carfilzomib Administration

Carfilzomib for Injection is supplied as a lyophilized parenteral product in single-use vials. The lyophilized product is reconstituted with Water for Injection to a final carfilzomib concentration of 2.0 mg/mL prior to administration. The dose will be calculated using the subject's actual BSA at baseline. Subjects with a BSA > 2.2 m² will receive a dose based upon a 2.2 m² BSA. Dose adjustments do not need to be made for weight gains/losses of \leq 10%. Subjects with a Body Surface Area (BSA) of greater than 2.2 m² will receive a capped dose of 44 mg of carfilzomib (at the 20mg/m^2 dose level), 123.2mg of carfilzomib (at the 56mg/m^2 dose level), or 154 (at the 70mg/m^2 dose level).

Carfilzomib will be given as an IV infusion over 30 minutes on Days 1, 8, and 15 of a 28-day cycle. If the subject has a dedicated line for carfilzomib administration, the line must be flushed with a minimum of 20 mL of normal saline prior to and after drug administration. The dose will be administered at a facility capable of managing hypersensitivity reactions. Subjects will be prehydrated with 250mL normal saline or other appropriate IV fluid formulation on cycle 1 Day 1. Other hydration procedures will be optional and per the discretion of the treating physician. Subjects will remain at the clinic under observation for at least 1 hour following each dose of carfilzomib in Cycle 1 and following the dose on Cycle 2 Day 1. Subjects should be monitored periodically during this period for evidence of fluid overload. Serum chemistry values, including creatinine, must be obtained and reviewed prior to each dose of carfilzomib during Cycles 1 and 2. Refer to Table 6-1 for guidance regarding dose reduction in subjects with compromised renal function.

Doses of carfilzomib may be rescheduled up to 2 days if the scheduled day falls upon a holiday or with approval from the Lead Principal Investigator. Missed doses will not be replaced during a cycle. Carfilzomib will be escalated from 20mg/m^2 (Cycle 1 Day 1) to 56mg/m^2 (Cycle 1 Day 8 and 15 see below) and then further escalated to 70mg/m^2 (Cycle 2 Day 1) as long as the subject does not present with cytokine release symptoms (fever, rash, dyspnea, etc) after Cycle 1 Day 2.

- Cycle 1: 20 mg/m² Day 1; 56 mg/m² Day 8; 56mg/m² Day 15.
- Cycles 2 8: 70mg/m^2 if tolerated Days 1, 8, and 15
- Cycles 9+ (for up to 24 cycles max): 70mg/m² if tolerated Days 1 and 15

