6.6. Dose-Modification Guidelines

The following sections and tables summarize dosing modifications of elotuzumab, carfilzomib, lenalidomide, and dexamethasone to manage possible toxicity. Dose modifications different from those stated in the protocol should be discussed with the Lead Principal Investigator. Administration of carfilzomib and lenalidomide will be discontinued in the event of any other toxicity that, in the opinion of the Lead, Secondary Site, or Treating Investigator, warrants discontinuation.

In addition to dose reductions, administration of elotuzumab, carfilzomib and lenalidomide will be held temporarily in the event of a treatment-related toxicity at the Treating Investigator's discretion. Study treatment may be reintroduced if resolution of the event to the baseline value or to \leq Grade 1 within 21 days; otherwise study drug will be permanently discontinued. Any deviations from this plan must be approved by the Lead Principal Investigator.

If a subject's elotuzumab administration is delayed on day 1 of a cycle, carfilzomib, lenalidomide, and dexamethasone will also be delayed until the elotuzumab is resumed, which would then become the new day 1 of that cycle.

If a subject's elotuzumab is held in the middle of a cycle, carfilzomib, dexamethasone, and lenalidomide dosing will continue as scheduled. If the subject's elotuzumab is delayed during the cycle and is resumed within the designated window, (+/-3 days Cycles 1 and 2; +/-7 days Cycles 3 and beyond) the subject may receive the scheduled dose. If the elotuzumab is not resumed within the given window (+/-3 days Cycles 1 and 2; +/-7 days Cycles 3 and beyond), the subject is to omit that dose, and resume dosing at the next dosing time point.

If a study drug (except dexamethasone) is discontinued, the subject may continue on trial. However, if the discontinuation happens prior to the end of cycle 8 (1^{ary} endpoint), the subjects will Page 45

continue to be treated and will only be included on the intent to treat analysis.

All clinically-significant non-hematologic toxicities must be resolved to Grade 1 or baseline.

Dose reduction levels of elotuzumab, carfilzomib, lenalidomide, and dexamethasone for toxicity management of individual subjects are provided below:

Table 6-1 Carfilzomib Dose Adjustments

Nominal carfilzomib dose	Dose -1	Dose -2	Dose -3	Dose -4
70 mg/m^2	56 mg/m^2	45 mg/m^2	36 mg/m^2	27 mg/m^2

Table 6-1 Lenalidomide Dose Adjustments

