6.10.4. Renal Function

Carfilzomib has not been fully characterized in subjects with creatinine clearance < 30 mL/min. It is critical that the subject's renal function is known at the time of dosing. Renal function, serum creatinine, and serum uric acid should be monitored closely during treatment with carfilzomib. Renal function must be monitored closely during treatment with carfilzomib. Serum chemistry values, including creatinine, must be obtained and reviewed prior to each dose of carfilzomib during Cycles 1 and 2. Refer to Table 6-7 for guidance regarding dose reduction in subjects with compromised renal function.

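### Table 6-6 tells sites both to hold elotuzumab and to give it at full dose when serum creatinine exceeds 2 mg/dL, without saying which row governs

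*Combined protocol and SAP*

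**What the plan says.** In the renal block of Table 6-6, the row "Serum creatinine > 2 mg/dL" sends lenalidomide and carfilzomib to the clearance rows ("Base dose reduction on calculated GFR (below"). The elotuzumab cell in that row does not defer. It reads "Hold Upon resolution elotuzumab can be" and, after a page break, "restarted at the treating physician's discretion".

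Four clearance rows follow: above 60, 30 to 60, below 30, and "CrCl< 30 mL/min requiring dialysis". Each gives elotuzumab at full dose.

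Section 6.6 says what follows if elotuzumab is delayed on Day 1 of a cycle: "carfilzomib, lenalidomide, and dexamethasone will also be delayed until the elotuzumab is resumed". Section 6.6.2.1 repeats the rule, and the elotuzumab dose-adjustment text under 6.6 agrees and sets a 21-day maximum delay.

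Two sentences point to renal dosing guidance. Section 6.4.2 says "Refer to Table 6-1 for guidance regarding dose reduction in subjects with compromised renal function", and section 6.10.4 says "Refer to Table 6-7 for guidance regarding dose reduction in subjects with compromised renal function".

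**The concern.** A site with a subject above 2 mg/dL finds two elotuzumab instructions in adjacent rows and nothing to choose between them. One site may hold the antibody and another may give it, and each can claim to follow the table or be cited for departing from it. Sections 1.6 and 4.2 present the dose modifications as obligatory, so this is more than loose guidance.

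Two things are at stake: consistent safety management of renal impairment across five centers, and, when the hold falls on Day 1, the timing of all four drugs. The two pointers do not help. The tables labelled 6-1 list dose levels and have no renal rows, and there is no Table 6-7, since the numbering passes from 6-6 to 6-8.

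**Working it through.** The plan gives no figure to reproduce here. The check sets the rows side by side and then tests whether one subject can meet two of them.

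**1. The rows of Table 6-6 (summarised)**

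| Row | Lenalidomide | Carfilzomib | Elotuzumab |
|---|---|---|---|
| Creatinine > 2 mg/dL | use rows below | use rows below | hold, restart on resolution |
| CrCl > 60 | full | full | full |
| CrCl 30–60 | reduced | full | full |
| CrCl < 30 | reduced | held | full |
| CrCl < 30, dialysis | reduced | held | full |

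For lenalidomide and carfilzomib the first row only directs the reader onward, so no conflict arises. For elotuzumab it is an instruction in its own right, and every later row differs from it.

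**2. Can one subject meet both?** Section 5.1 gives Cockcroft-Gault: CrCl = (140 − age) × weight × k / (72 × creatinine), with k = 1.00 for men and 0.85 for women. The ages and weights below are my assumptions. At creatinine 2.1 mg/dL the denominator is 72 × 2.1 = 151.2.

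- Man, 40 years, 100 kg: 100 × 100 / 151.2 = 66.1 mL/min (row above 60).
- Man, 70 years, 75 kg: 70 × 75 / 151.2 = 34.7 mL/min (row 30–60).
- Woman, 65 years, 70 kg: 75 × 70 × 0.85 / 151.2 = 29.5 mL/min (row below 30).

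Each subject is told to hold by the creatinine row and to receive full dose by the clearance row. The overlap does not depend on these examples, because every listed band says full dose. Only clearances of exactly 30 or 60 have no row.

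**3. Can it arise at entry?** The renal criterion in 5.1 is creatinine ≤ 1.5 × ULN or CrCl ≥ 50 mL/min. The same assumed 40-year-old, 100 kg man at 2.5 mg/dL has 10,000 / (72 × 2.5) = 10,000 / 180 = 55.6 mL/min. He meets the renal entry criterion and the hold row together. With a stable value above 2 mg/dL, the row does not say what would count as resolution.

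**4. What does a hold do to the other drugs?**

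- Day 1: they are delayed (6.6, the elotuzumab dose-adjustment text, 6.6.2.1).
- Mid-cycle: 6.6 and 6.6.2.1 continue them on schedule, while the elotuzumab dose-adjustment text leaves the decision for Days 8, 15 and 22 to the treating investigator. These passages do not agree.

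**5. What does the conflict add to existing rules?** Section 6.5 already prevents a new cycle while a drug-related event remains above grade 1 or baseline, and requires creatinine to be back at baseline before carfilzomib in Cycles 1 and 2. A drug-related rise on Day 1 can therefore delay the cycle whichever elotuzumab row is read. The conflict makes its own difference mainly for elevations that are not drug-related or are at baseline, and for mid-cycle doses.

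**The case against.** The best defence reads the rows in sequence: hold at creatinine above 2 mg/dL, then restart unreduced, since elotuzumab has no dose reductions. In support, the column is headed as recommended action, 6.6 sends departures to the Lead Principal Investigator, and 6.6.2.1 ties elotuzumab delays to toxicity considered related to elotuzumab.

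This does not remove the conflict. Where the clearance rows intend a hold they say so, as the carfilzomib cell below 30 mL/min does. In the same rows, full dose for carfilzomib plainly means that the drug is given. The creatinine row carries no attribution condition, unlike the later row for toxicity assessed as elotuzumab-related. Section 6.6 does have a general standard of return to baseline or grade 1 for treatment-related toxicity, but the creatinine row is not linked to it. A subject whose baseline exceeds 2 mg/dL would satisfy that standard and still trigger the row.

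The defence is right about consequences. A reader might infer that any elotuzumab hold stops all four drugs, that affected subjects will leave treatment before the end of cycle 8, and that the primary rate will differ between sites. The documents do not support these readings:

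- The all-drug delay follows only from a Day 1 hold, and 6.5 would cause part of that delay anyway.
- The 21-day limit can be waived (6.5, 6.9). A subject who stops one study drug other than dexamethasone may stay on trial and in the intent-to-treat analysis (6.6).
- No frequency of creatinine above 2 mg/dL on treatment is given, and the primary analysis in 10.2.1 is one pooled exact binomial test in 40 subjects. One subject is 1/40 = 2.5 percentage points, but nothing shows that any response would change.

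It is also unnecessary to claim that creatinine above 2 mg/dL nearly always means clearance below 60, since the row above 60 conflicts as well. The two misdirected pointers concern carfilzomib, whose renal cells do not conflict. They are a separate, lesser error.

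**Conclusion.** The contradiction is in the current text and needs correction. It is not a reading artefact: the hold cell crosses a page break, but its continuation is present. It covers essentially every subject with creatinine above 2 mg/dL. This rests on the table as printed; the assumed ages and weights only illustrate the overlap.

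Its practical reach is narrower than a first look suggests. It is mainly elevations that are not drug-related or are already at baseline, and mid-cycle doses, with the all-drug delay confined to Day 1 holds. How many subjects would be affected cannot be derived from the documents. An effect on the primary rate is possible but not shown, and the stated test and sample size are untouched.

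**What to change.** The clinical team should:

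- reconcile the elotuzumab cells of the renal rows in Table 6-6, so that one instruction applies to any given creatinine and clearance, and state which row governs;
- define resolution for the creatinine row, including for a subject whose baseline is above the threshold;
- reconcile the mid-cycle hold rules in 6.6, the elotuzumab dose-adjustment text and 6.6.2.1;
- redirect the pointers in 6.4.2 (to Table 6-1) and 6.10.4 (to the non-existent Table 6-7) to the renal rows of Table 6-6.

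Which instruction is right is a clinical decision and is not proposed here. The cost is a table and text correction in an amendment or a clarification letter to the sites, with no change to sample size or analysis.
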